 - ii. Describe reasons for discontinuation of CAB LA PrEP
 - iii. Describe characteristics of the individuals who discontinue CAB LA PrEP
- 3) Effectiveness: Monitor for incidence of HIV diagnoses while on CAB for PrEP and describe the timing of incident HIV diagnoses with respect to timing of CAB for PrEP usage
 - a. Describe the proportion and number of incident HIV-1 infections while on CAB for PrEP among individuals in the following groups:
 - i. Infected during OLI
 - ii. Infected while on CAB LA: Incident HIV diagnoses, defined as HIV diagnosed after start of CAB injections while adhering to CAB LA PrEP regimen
 - b. Describe the timing of diagnosis of HIV with respect to timing of CAB for PrEP usage among individuals in the following groups:

- i. Infected during OLI
- ii. Infected while on CAB LA: Incident HIV diagnoses while adhering to CAB LA PrEP regimen
- c. Describe the proportion of incident infections among those who start with OLI and those who go to DTI separately and the timing of diagnosis of incident HIV for the overall group, and separately for the OLI and DTI groups.

The proposed study is a non-interventional study and will collect data from routine clinical practice and plans to capture all prevalent HIV-1 infections, including those captured during baseline. However, there are no plans to collect and store serum samples for subsequent testing as this is not part of standard of care.

- 4) Safety: Monitor for occurrence of DILI and HSRs following CAB LA injections
 - a. Describe the frequency of DILI after starting CAB LA at 6, 12, 24, 36, and >36 months after initiation as defined in Section 7.3.2.
 - i. Incidence proportion and rate of DILI following administration of CAB LA PrEP
 - ii. Incidence proportion and rate of CAB LA discontinuation due to DILI
 - b. Describe the frequency of HSR after starting CAB LA at 6, 12, 24, 36, and >36 months after initiation
 - i. Incidence proportion and rate of HSR following administration of CAB LA PrEP
 - ii. Incidence proportion and rate of CAB LA discontinuation due to HSR
- 5) Resistance: Evaluate incidence of and risk for developing resistance to integrase inhibitors (INSTI) among individuals in the following groups:
 - a. Incident HIV diagnoses while adhering to CAB LA for PrEP and development of resistance during treatment for HIV
 - b. CAB LA PrEP discontinued:
 - i. without subsequent oral PrEP & potential risk for HIV acquisition and viral resistance during CAB LA PK tail

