 - ii. switched to oral PrEP and acquire HIV during the remainder of the follow-up period and develop resistance during subsequent treatment with ARVs
 - c. Individuals with undiagnosed prevalent HIV at initiation of CAB PrEP and subsequent emergence of resistance while on CAB monotherapy

Resistance testing: Since this is a non-interventional study aiming to capture standard of care (SoC) in real world settings, the study will not mandate resistance testing following discontinuation of CAB LA for PrEP. Health care providers following the SmPC and applicable local guidelines will decide what laboratory and resistance tests are to be conducted while an individual is on CAB LA for PrEP. Data thus generated, including available HIV-1 subtypes, will be captured

and analysed by the study team. Resistance will also be assessed among the individuals who are non-adherent to the injection regimen and acquire HIV.

7. **RESEARCH METHODS**

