- b) Individuals with undiagnosed prevalent infections at the time of CAB PrEP initiation
- c) Durability of INSTI-based vs. non-INSTI based regimens (e.g., the numbers and proportions of those who achieve and maintain virologic suppression, the time to virologic suppression, the time to virologic breakthrough), as well as any INSTI resistance-associated substitutions that are detected upon ART failure

5) Adherence and Durability

- a) Adherence to CAB LA PrEP including OLI will be estimated from data collected via health record data
- b) Non-adherence to the dosing schedule will be assessed by:
 - Estimating the number of individuals that missed one or more consecutive injections without taking daily oral PrEP bridging while not on CAB LA injections and mean and median number of injections missed during a 6 and a 12-month period
 - Estimating the number of individuals who received the injections seven or more days later than their scheduled injection visit and median duration of delayed injections
 - Estimating the number of individuals who missed one or more consecutive injections without taking daily oral PrEP bridging or those who received the injections seven or more days later than their scheduled injection visit (Combined group a OR b) and describe characteristics for the individuals that are nonadherent
- c) Discontinuation will be defined as 2 injection cycles (~127 consecutive days) in which no injections were administered without oral PrEP bridging
- d) Describe the frequency and the regimen used for oral PrEP bridging to cover planned delayed or missed injections
- 6) Frequency of resistance to INSTIs and specific mutations among the following groups:
 - a) CAB LA PrEP started when the individual had undiagnosed HIV and subsequent emergence of resistance while on CAB monotherapy
 - b) CAB LA PrEP discontinued
 - without subsequent oral PrEP & potential risk of HIV acquistion and viral resistance during CAB LA PK tail
 - switched to oral PrEP and acquire HIV during the follow-up period and develop resistance during subsequent follow-up period while on treatment with ARVs
 - c) Incident HIV diagnosis while adhering to CAB LA for PrEP and development of resistance during treatment for HIV
- 7) Frequency of DILI and HSRs following CAB OLI and CAB LA injections assessed at 6, 12, 24, 36, and >36 months.

Hepatotoxicity related to administration of CAB for PrEP (i.e., DILI) as described below will be tabulated:

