ART regimen and VL testing among CAB PrEP users with undiagnosed prevalent infections and incident infections will be described separately, during the follow-up period. In the event of a delay of ART initiation post HIV diagnosis, the study will strive to follow the individual after ART initiation and through the end of the follow-up period. Durability of INSTI-based vs. non-INSTI based regimens (e.g., the numbers and proportions of those who achieve and maintain virologic suppression, the time to virologic breakthrough), as well as any INSTI resistance-associated substitutions that are detected upon ART failure will also be assessed and reported.

Analysis for Objective 4 (Safety: Monitor for occurrence of DILI and HSR)

Proportion and number of individuals with DILI and HSRs following CAB OLI and CAB LA injections will be shown separately at 6, 12, 24, 36 months after initiation and over the entire length of the follow-up period. Proportion and number of individuals discontinuing CAB OLI and CAB LA PrEP due to DILI or HSR will be shown at 6, 12, 24, 36 months and over the entire length of the follow-up period. Discontinuation of CAB LA PrEP or CAB OLI will be based on medical records indicating date when discontinuation decision was made by a physician and will be reviewed and confirmed by an independent adjudication committee. Frequency of hepatotoxicity and HSR events will be reported separately for OLI period and during injections.

Analysis for Objective 5 (Resistance monitoring)

Proportion and number of individuals developing drug resistance to INSTIs based on genotypic data will be assessed among the 4 different groups as follows:

a) Individuals with undiagnosed prevalent HIV, initiating CAB OLI or CAB LA PrEP, will be followed through the end of the follow-up period after ART initiation and will be monitored for resistance

- b) Individuals with incident HIV while on CAB LA PrEP will be followed through the end of the follow-up period following ART initiation and monitored for resistance
- c) Individuals who discontinue CAB LA PrEP will be followed through the end of the follow-up period and if they acquire HIV will continue to be followed after ART initiation to monitor for resistance
- d) Individuals who switch to oral PrEP and acquire HIV during the 12- month follow-up period while on oral PrEP will be followed through the end of the follow-up period after ART initiation and monitored for resistance

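### Objective 5 counts INSTI resistance as emerging on cabotegravir, but requires no earlier genotype for comparison and follows prevalent cases only from ART start

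*Protocol*

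**What the plan says.** For people who already had undiagnosed HIV when they started cabotegravir, Objective 5(c) in section 6 names "Individuals with undiagnosed prevalent HIV at initiation of CAB PrEP and subsequent emergence of resistance while on CAB monotherapy". Outcome 6(a) in section 7.3.2 repeats the idea: "CAB LA PrEP started when the individual had undiagnosed HIV and subsequent emergence of resistance while on CAB monotherapy". The heading above that outcome is plainer: "Frequency of resistance to INSTIs and specific mutations among the following groups". The analysis text in section 7.6.1 returns to the language of change: "Proportion and number of individuals developing drug resistance to INSTIs based on genotypic data will be assessed among the 4 different groups".

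The other groups are worded differently. Objective 5(a) reads "Incident HIV diagnoses while adhering to CAB LA for PrEP and development of resistance during treatment for HIV", and 5(b)(ii) reads "switched to oral PrEP and acquire HIV during the remainder of the follow-up period and develop resistance during subsequent treatment with ARVs". Objective 5(b)(i), on people who stop injections without oral PrEP, links resistance to the pharmacokinetic tail but does not speak of emergence.

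On the data behind these outcomes, section 6 states that "there are no plans to collect and store serum samples for subsequent testing as this is not part of standard of care" and leaves the choice of resistance tests to the treating provider. Section 7.5 places resistance and subtype results from the time of HIV acquisition on the collection form. Section 7.1 starts the follow-up of prevalent cases at ART start, and group (a) in section 7.6.1 monitors them for resistance after ART initiation.

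**The concern.** To say that resistance emerged or developed is to claim a change: the mutation was absent in an earlier genotype and present in a later one from the same person. The protocol uses this language but sets no comparison genotype, and gives no rule for a mutation already present the first time the virus is sequenced. For prevalent cases the follow-up window is also misplaced, because the outcome concerns cabotegravir alone while the described monitoring begins with or after ART.

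Section 5.2 names resistance in people with unrecognised infection at the start of cabotegravir as one of the risks behind the study. A mutation tabulated under 5(c) will therefore be read as evidence on that risk. The numbers will be small, so a single case with the wrong label can change what the table appears to show.

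**Working it through.** The protocol gives no figure for resistance, so there is nothing to reproduce. The check sets the passages side by side and then gauges the weight of one case.

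**1. What each group's wording needs**

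| Group | Period in which resistance is placed | Earlier genotype needed to show change | Required by the protocol? |
|---|---|---|---|
| 5(c) and 6(a), prevalent HIV | On cabotegravir, before ART | Initiation sample or first positive sample | No; captured if done in routine care |
| 5(b)(i), stopped without oral PrEP | Loosely, the drug tail | First positive sample | No; captured if done |
| 5(a) and 6(c), incident HIV | HIV treatment | Genotype at diagnosis | No; captured if done |
| 5(b)(ii), switched to oral PrEP | HIV treatment | Genotype at diagnosis | No; captured if done |

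**2. Where a detected mutation can come from**

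- First genotype before ART: carried by the acquired virus, or selected by cabotegravir.
- First genotype after ART start: either of these, or selected by ART. Section 7.3.2 item 4(c) expects some regimens to be INSTI-based, so the last route is open.

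In a prevalent case, 5(c) concerns only selection by cabotegravir. The count "Proportion and number of individuals developing drug resistance to INSTIs based on genotypic data" is not split by sample timing, so as written it can mix all three sources.

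**3. How the protocol treats baseline elsewhere**

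In section 7.3.2, abnormal liver tests before cabotegravir change the reference value for DILI, and a committee judges attribution. The same section separates prevalent from incident HIV by sample date. Resistance has no equivalent rule, and section 7.8 does not list the gap.

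**4. Weight of one case**

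Inputs: at least 500 participants (section 7.4.1); at least 3 years of follow-up (section 7.6.1); 0.20 and 0.40 infections per 100 person-years on cabotegravir in the two pivotal trials (section 5.1). Assumptions: no loss to follow-up, and every infection genotyped.

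- Person-years: 500 × 3 = 1,500.
- Expected incident infections: 1,500 × 0.20/100 = 3; 1,500 × 0.40/100 = 6.
- Shift in a proportion from one misclassified case, 1/k: 1/3 = 33 points; 1/6 = 17 points.
- If everyone were followed for 5 years: 2,500 × 0.20/100 = 5 and 2,500 × 0.40/100 = 10 infections, so shifts of 20 and 10 points.

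These are incident cases. The protocol gives no expected number of prevalent cases, so no such figure can be worked out for 5(c).

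**5. Chance of at least one such case (illustration only)**

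The share t of acquired virus already carrying an INSTI mutation is not in the protocol. Assume 0.1% to 5%. The chance of at least one among k infections is 1 − (1 − t)^k:

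- k = 3: 0.3% to 14%.
- k = 6: 0.6% to 26%.

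The result is driven by the assumption. It shows that the event may be uncommon, not how common it is.

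**The case against.** The best defence is that this is a non-interventional study whose outcome heading is a plain frequency, and whose tables list mutations and subtype by group without any causal estimate. Several stronger readings that a reader might infer do fail:

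- *That pre-existing resistance is attributed to cabotegravir.* No passage says so. The wording permits a mutation to be counted as emergent without showing that it emerged.
- *That there is no genotype from before cabotegravir.* For prevalent cases the defining sample is taken at initiation, and a routine genotype of it would be captured. Section 7.2.1 also asks sites about resistance testing. The accurate statement is that none is required.
- *That the lack of such a genotype is a fault in incident cases.* Incident cases are RNA-negative at the start, so none can exist.
- *That all of Objective 5 concerns resistance arising on cabotegravir.* Objectives 5(a) and 5(b)(ii) place development in the treatment period, where the genotype at diagnosis is the comparator.
- *That the allowance of 4 to 6 weeks for a prevalent result puts the genotype after dosing.* Section 7.3.2 explains it as time for results to be obtained, confirmed and uploaded, with the sample date governing classification.

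It can also be said that classification rules belong in the SAP, and section 7.6.1 does promise a description of the resistance methods. That holds for table layout and the handling of individual mutations. It does not hold for the outcome label or the follow-up window, which the protocol itself fixes. An SAP could relabel the result but could not create a missing earlier genotype.

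**Conclusion.** The point holds as one of outcome definition. In 5(c) and 6(a), and loosely in 5(b)(i), the protocol names an outcome that a first genotype, or one first taken after ART start, cannot establish. For 5(a) and 5(b)(ii) the gap is narrower: a genotype at diagnosis is the needed comparator, and it is collected only if routine care produces it.

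The size of the error cannot be computed from the protocol, which gives neither the number of prevalent cases nor the share of acquired virus with INSTI mutations. With 3 to 6 incident infections, one misclassified case is worth about 33 to 17 points. That rests on the pivotal-trial rates applying here, no loss, and every infection genotyped; with fewer genotyped, each case weighs more. A reader might infer that the reported proportion will certainly be too high. The documents do not support that: they show that wrong counting is possible, not that it will occur.

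**What to change.** Change the wording in Objective 5, outcome 6 and the Objective 5 analysis in section 7.6.1:

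- Report INSTI mutations detected. For each, give the sample date relative to first cabotegravir dose and ART start, and the number of injections before the sample. Report how many people were genotyped at each stage.
- Keep the words emergent and developing for mutations absent in an earlier genotype of the same person, using a routine genotype of the initiation or first positive sample where one exists. Split these into before and after ART start.
- Show all others separately as present at first genotype, origin undetermined.
- Align the follow-up window for prevalent cases in sections 7.1 and 7.6.1 with 5(c), so that it includes the time between first cabotegravir dose and ART start.
- State the limit in section 7.8.

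The cost is small. No test, sample or change to care is added. Genotype sample dates must be captured, since section 7.5 names injection dates and resistance data but not these. Some cases will be labelled origin undetermined, including some that cabotegravir may in fact have selected; showing their timing keeps them visible.

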7.1. Study Design

This will be a 5-year long prospective cohort study of adult and adolescents \geq 35 Kgs, initiating CAB LA for PrEP, in real world clinical settings across Europe. All treatment decisions will be made by the healthcare provider per guidelines for CAB LA for PrEP and SmPC. This study will use deidentified data from individual electronic medical records from participating clinical sites.

- All CAB LA for PrEP users will be followed for at least 3 years from the time of initiation while on CAB LA PrEP
- Individuals with an incident HIV diagnosis will be followed from the start of ART and their virologic suppression and emergence of resistance to ARVs through the end of the study follow-up period, and cross resistance to other integrase inhibitors will be monitored
- Individuals initiating CAB PrEP with undiagnosed prevalent HIV-1 infection will be followed from the start of ART and their virologic suppression and emergence of resistance to ARVs through the end of the study follow-up period, and cross resistance to other integrase inhibitors will be monitored
- Participants discontinuing CAB LA PrEP will be monitored for HIV acquisition and, if diagnosed, will be monitored for ARV effectiveness & potential emergence

of resistance as per SoC/local guidelines through the end of the study follow-up period

• Testing for incident HIV & resistance: Testing frequency for HIV and resistance if needed, is expected to be per guidelines for LA PrEP and SmPC

7.2. Study Population and Setting

7.2.1. Study Setting

Potential investigational sites within the NEAT-ID Network across Europe will be contacted for feasibility and resistance testing practices as part of their SoC. A formal feasibility assessment questionnaire will be conducted after the protocol is finalized and approved and will be used to determine sites' eligibility to participate in the study. This formal feasibility assessment will include assessing site's infrastructure to participate in research studies, number of any PrEP prescriptions in the previous year, availability of resistance testing, and HIV testing practices per local standard of care practices. Followup period will start from the date of the first participant enrolled in the study and will end five years after the date of first enrolment.

Participant data will be collected via extraction from electronic medical records (i.e., source data) by appropriately trained and authorized member(s) of the study team who must be identified and authorized in writing by the Principal Investigator (PI). A delegation of responsibility log will be maintained accordingly. In order to maintain confidentiality, the participants will be identified only by study number.

All data will be entered directly into the electronic data capture (EDC) by the sites and will be checked for completeness every 6 months by the data coordinating center. NEAT-ID's management team will store the data on a secure network drive with access to authorized personnel of the data management team only, maintained on a log of authorized personnel by the data coordinating center.

NEAT-ID team will perform site management activities to assess protocol issues, consent, data quality and study management quality performance.

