7.4.1. Study size

The study is not a hypothesis testing study, but it is designed to assess usage of CAB LA for PrEP in real world clinical settings. The overall number of participants in this cohort study will depend on the uptake of the CAB LA for PrEP and how widely it will be used across the NEAT-ID clinical sites.

The study aims to include a target of at least 500 participants initiating CAB LA for PrEP. There is no formal statistical hypothesis to be tested in these analyses. Table 1 below gives an indication of the likely precision of the estimates of the proportion with incident HIV, using Exact Clopper Pearson confidence limits under different scenarios.

Confidence Level	Sample Size (N)	CI Width	Incident HIV rate (%)	Lower Limit	Upper Limit
0.95	500	1.1824	0.25	0.0118	1.1942
0.95	500	1.5093	0.50	0.0832	1.5925
0.95	500	1.9926	1.00	0.3255	2.3181
0.95	500	2.3679	1.50	0.6283	2.9962
0.95	500	2.6841	2.00	0.9631	3.6472
0.95	500	2.9617	2.50	1.3185	4.2802
0.95	1000	0.7568	0.25	0.0416	0.7984
0.95	1000	1.0004	0.50	0.1625	1.1629
0.95	1000	1.3507	1.00	0.4806	1.8313
0.95	1000	1.6201	1.50	0.8419	2.4620
0.95	1000	1.8462	2.00	1.2258	3.0720
0.95	1000	2.0442	2.50	1.6243	3.6685
0.95	2000	0.5012	0.25	0.0812	0.5824
0.95	2000	0.6776	0.50	0.2400	0.9176
0.95	2000	0.9283	1.00	0.6119	1.5402

Table 1: Precision estimates

CONFIDENTIAL

CTMS Project Number: 221935 Final Protocol

				-	
0.95	2000	1.1202	1.50	1.0143	2.1345
0.95	2000	1.2810	2.00	1.4326	2.7136
0.95	2000	1.4217	2.50	1.8611	3.2828

Table 2 below shows the precision estimates for regimen discontinuation rates varying from 2.5% to 20% for a sample of 500 individuals.

Confidence Level	Sample Size (N)	CI Width	Discontinuation rate	Lower Limit	Upper Limit
0.95	500	0.0296	0.025	0.0132	0.0428
0.95	500	0.0403	0.050	0.0326	0.0729
0.95	500	0.0546	0.100	0.0751	0.1297
0.95	500	0.0646	0.150	0.1198	0.1844
0.95	500	0.0720	0.200	0.1658	0.2378

 Table 2. Precision estimates by discontinuation rate

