7.5. Data management

Following the availability of CAB LA for PrEP in Europe, the study will collect followup data prospectively on a target of at least 500 individuals initiating CAB LA for PrEP, for a follow-up period of at least 3 years. Participants who discontinue CAB LA for PrEP will be followed up through the end of the follow-up period after discontinuation.

The NEAT-ID Network coordinating centre will receive data from the clinical sites per the protocol for the study. A detailed data collection form will be used to collect comprehensive data needed for study analysis, including clinical sites including dates of injections, clinical and laboratory parameters (immunologic, biochemistry, haematology and pathology), resistance and HIV subtype data at HIV acquisition, and after discontinuation and switching to another PrEP regimen.

In order to maintain confidentiality, the subject will be identified only by subject number. Subject data will be collected via extraction from individual medical record as source data by appropriately trained and authorised member(s) of the study team who must be identified and authorised in writing by the Principal Investigator (PI). A delegation of responsibility log will be updated accordingly.

Sites will provide and upload data to the data management team who will store the data on a secure database with access to authorised personnel of the study management team only, maintained the log of authorised personnel by the sponsor representative.

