7.6. Data analysis

7.6.1. Essential analysis

Specific analytic methods are shown for each study objective. All CAB LA PrEP users will be followed for at least 3 years (36 months). All individuals with incident HIV acquisition will be followed through the end of the follow-up period. Participants discontinuing CAB LA PrEP will be monitored through the end of the follow-up period for HIV acquisition and, in the case of HIV acquisition, will be monitored for ART effectiveness and potential emergence of resistance.

In the event of a delay of ART initiation post HIV diagnosis, the study team will strive to follow the individual through the end of the follow-up period. Interim results will be generated at 12, 24, 36, 48 months since study initiation and final results will be generated at 60 months since study initiation.

Analysis for Objective 1 (Description of CAB for PrEP Usage pattern)

For individuals initiating CAB for PrEP, baseline demographics (age, sex, gender, ethnic origin (where available), BMI, geographic region), history of previous PrEP use and use of OLI prior to initiating injections will be described. Comorbidities, STIs, risk factors for HIV acquisition (e.g. HIV status of sexual partner, multiple sexual partners), will be reported as frequencies at baseline and at 6, 12, 24, 36, and >36 months of follow-up as available. Proportion of individuals using oral PrEP to cover planned, delayed or missed CAB LA injections will also be provided. Frequency of testing for HIV once initiated CAB for PrEP will be evaluated, and timing of HIV testing relative to injection dates will be assessed.

Prevalent HIV is defined as any undiagnosed HIV at the time of PrEP initiation and will be defined as positive HIV antigen/antibody test and/or positive viral load from sample collected at the time of initiation (first prescription of CAB oral lead and, separately, first CAB LA PrEP injection). Note the test result may be reported within 4-6 weeks after the sample was collected. Prevalent HIV will be reported at baseline while on CAB OLI and while on CAB LA. Also, prevalent HIV will be reported for those who received CAB OLI and separately for those with direct to injection (DTI) strategy. Incident HIV is any new HIV diagnosis that occurs after the initiation of CAB PrEP, having confirmed HIV negative status using HIV RNA test, at the time of PrEP initiation. Incident HIV reporting is described in objective 3.

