7.8. Limitations of the research methods

Limitations of this study are common to non-randomized, non-interventional observational cohort studies. This is a study of routine clinical care and reflects treatment practice across NEAT-ID Network clinical sites. Confounding by indication, whereby persons are selected for specific regimens, cannot be ruled out. While the study aims to include a target of at least 500 individuals initiating CAB LA for PrEP, market uptake of the regimen and individuals' willingness to participate will dictate how quickly data will be collected.

Follow-up of study participants through the end of the follow-up period after discontinuation of CAB LA for PrEP or after HIV acquisition will increase the potential for loss to follow-up as would be expected, in a real-world setting. The results from this study should be interpreted cautiously, with careful consideration given to the limitations of the observational study design.

8. **PROTECTION OF HUMAN SUBJECTS**

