11. PLANS FOR DISSEMINATING AND COMMUNICATING STUDY RESULTS

11.1. Target Audience

This study-specific protocol will be submitted for EMA's review and endorsement. The study will start once CAB LA for PrEP is commercially available in Europe and is expected to continue through 2029 or later. Annual interim reports with cumulative data will be submitted and a final report is expected to be submitted in July 2030.

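### A three-year minimum follow-up for all users fits a close five years after first enrolment only if everyone enters by month 24, which no visible text secures

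*Protocol*

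**What the plan says.** Three sections give a minimum follow-up. Section 7.1: "All CAB LA for PrEP users will be followed for at least 3 years from the time of initiation while on CAB LA PrEP". Section 7.5 applies the minimum to the target of at least 500 individuals, "for a follow-up period of at least 3 years". Section 7.6.1 repeats it for all users, as 36 months and without the on-treatment qualifier.

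Section 7.2.1 sets a fixed close. Follow-up starts with the first participant enrolled and "will end five years after the date of first enrolment". Section 7.6.1 adds that "final results will be generated at 60 months since study initiation".

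On entry, section 7.3.1 includes all new users and gives no cut-off. Section 7.4.1 makes the number enrolled depend on uptake, with a target of at least 500. Section 7.8 says that uptake and individuals' "willingness to participate will dictate how quickly data will be collected".

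On analysis, the primary effectiveness measure in section 7.6.1 is the proportion with incident HIV diagnosis at 6, 12, 24 and 36 months and over all follow-up. Discontinuation, drug-induced liver injury (DILI) and hypersensitivity reactions (HSR) are also reported as numbers and proportions at these times. On precision, section 7.4.1 says "Table 1 below gives an indication of the likely precision of the estimates of the proportion with incident HIV". Neither Table 1 nor Table 2 names a time point.

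**The concern.** The close is tied to the first participant and the minimum to each participant. A fully persistent user who enters at month 30 can be observed for at most 30 months, so the on-treatment qualifier in section 7.1 does not remove the conflict. Late entry becomes more likely if uptake is slow, and section 7.8 acknowledges that uptake sets the pace.

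Two things are at stake. First, the stated minimum follow-up is a property that the visible design does not guarantee. Second, the 36-month proportions, including the primary effectiveness measure, would rest on fewer people than enrolled. If participants with less than 36 months of potential follow-up stayed in a simple month-36 denominator, they would count as event-free for time in which nobody observed them. The proportions with HIV diagnosis, discontinuation, DILI and HSR would then be biased downward.

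**Working it through.** **Inputs.** Minimum follow-up of 36 months (sections 7.1, 7.5, 7.6.1). Close 60 months after first enrolment (7.2.1). Target of at least 500 (7.4.1). No accrual rate or loss rate is given.

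**Step 1: reproduce the plan's own precision figures.** The exact (Clopper-Pearson) limits are L = Beta quantile(0.025; x, n − x + 1) and U = Beta quantile(0.975; x + 1, n − x), with x = n × p and fractional x allowed.
- Table 1, n = 500, p = 1%, x = 5: 0.3255% to 2.3181%, width 1.9926 points, as printed.
- Table 2, n = 500, p = 20%, x = 100: 0.1658 to 0.2378, width 0.0720, as printed.
- All 18 rows of Table 1 and all 5 rows of Table 2 reproduce. The only difference is one fourth decimal (0.0119 computed, 0.0118 printed).

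The tables are therefore correct intervals in which all N are observed.

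**Step 2: latest entry compatible with each time point.** Latest entry = 60 − time point.
- Month 36: 60 − 36 = month 24
- Month 24: 60 − 24 = month 36
- Month 12: 60 − 12 = month 48
- Month 6: 60 − 6 = month 54

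Two conditions follow for month 36. The three-year minimum for all users needs every entrant by month 24. A month-36 proportion with n = 500 needs only that at least 500 enter by month 24, and that none of those 500 is lost.

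**Step 3: effect of later entry (assumed accrual).** The protocol gives no accrual pattern, so a range is shown. Assumptions: exactly 500 enrolled, uniform accrual over T months, no loss to follow-up. The share able to reach month 36 is min(1, 24/T).

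| T (months) | Share | n able to reach month 36 | Longest follow-up of last entrant (months) | Exact 95% CI at 1% HIV (%) | Width (points) | Width at 20% discontinuation (proportion) |
|---|---|---|---|---|---|---|
| 24 or less | 100% | 500 | 36 or more | 0.325 to 2.318 | 1.99 | 0.0720 |
| 30 | 80% | 400 | 30 | 0.273 to 2.540 | 2.27 | 0.0807 |
| 36 | 67% | 333 | 24 | 0.230 to 2.756 | 2.53 | 0.0887 |
| 48 | 50% | 250 | 12 | 0.167 to 3.167 | 3.00 | 0.1028 |
| 60 | 40% | 200 | 0 | 0.121 to 3.565 | 3.44 | 0.1153 |

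Loss to follow-up, which section 7.8 expects, would reduce these numbers further.

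**The case against.** The strongest reply is that a five-year study with at least three years per user simply implies last entry by month 24. On that reading the sections agree, and the deciding date may sit in the redacted part of the milestone table. This stands in part: the absence of an enrolment date cannot be called an omission. But the milestones are headed as estimated dates, and the readable sections include all new users and leave the pace to uptake. The text that states the minimum should also state the condition it depends on. Section 11.1, where the study is "expected to continue through 2029 or later", is looser than section 7.2.1 but does not replace its fixed close.

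Several stronger readings are tempting, and the document does not support them.

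- A reader might infer that Tables 1 and 2 are wrong, or hold only if 500 enrol within 24 months. They are arithmetically correct, are offered as indicative for a study that tests no hypothesis, and hold at any time point that 500 people reach. Only a month-36 reading after late entry would overstate precision.
- A reader might infer that the 20% discontinuation in Table 2 should shrink its denominator. Discontinuation is the outcome in that table, and sections 7.1, 7.5 and 7.6.1 keep discontinuers in follow-up.
- A reader might infer that late entrants will be counted as event-free. Nothing says so. The denominator may be defined in the SAP, which is not at hand, and the planned Kaplan-Meier curve for time to HIV diagnosis can use shorter follow-up. It is a possibility to be closed off. Section 7.6.1 names Kaplan-Meier only for that outcome, so it does not cover the other proportions.
- A reader might infer that month-36 results would be invalid. They would rest on fewer people.

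The accrual scenarios are assumptions. The 60-month case is an extreme that itself breaks the three-year commitment.

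**Conclusion.** The point holds as a conflict between stated rules that the visible text does not resolve. Three years for all users, inclusion of all new users, and a close 60 months after first enrolment cannot all hold for anyone who enters after month 24. If every participant enters by then, nothing is lost except clarity.

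If entry runs later, the effect falls on the simple month-36 proportions. With 500 enrolled uniformly over 36, 48 or 60 months, one third, one half or three fifths could not reach month 36. The interval width at a 1% HIV proportion would be about 1.3, 1.5 or 1.7 times the tabulated one (2.53, 3.00 or 3.44 divided by 1.99). Enrolment above 500 would soften the loss of precision, but each entrant after month 24 would still fall short of the stated minimum. The figures assume uniform accrual, exactly 500 participants and no loss to follow-up. The correction is worth making because the primary effectiveness measure is among the affected proportions and the remedy is cheap.

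**What to change.** 1. Reconcile sections 7.1, 7.2.1, 7.5 and 7.6.1. Either state that the last participant enters no later than month 24 after first enrolment, or limit the three-year minimum to participants enrolled by month 24 and describe the rest as followed to the study close.
2. Base each simple month-36 proportion on participants with at least 36 months of potential follow-up. Later entrants still contribute as censored observations to the Kaplan-Meier analysis and with their person-time to the rates, so their information is kept.
3. In section 7.4.1, state that Tables 1 and 2 assume all N are observed at the time point, and add rows for smaller numbers, for example 200 and 333.

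The cost is protocol wording and a few recomputed rows, with no extra participants. The downside is that the stated month-36 precision becomes less favourable. Choosing a last-entry date also means that slow uptake could leave fewer than 500 enrolled; the second option in item 1 avoids that but gives up the minimum for later entrants.
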